3.12.	Lens Removal	Have the subject remove the study lenses.	
		Temporarily store the worn lenses until	
		Biomicroscopy has been completed. If no	
		adverse event or PQC was recorded, the worn	
3.13.	Diamiaragaany	lenses may be discarded.	
3.13.	Biomicroscopy	FDA Slit Lamp Classification Scale will be used to grade the findings and determine	
		eligibility.	
		engionity.	
		If the clearance of the fluorescein needs to be	
		expedited, preservative-free rewetting drops	
		or saline may be instilled.	
3.14.	Insertion of Study	Provide the subject with a NEW PAIR of	
	Lenses	lenses that match the power of the lenses that	
3.15.	Exit Distance and	were discarded in step 3.12 above. Record the distance and near Snellen visual	
3.13.	Near Visual Acuity	acuity (OD, OS, OU) to the nearest letter with	
	1 Tour Vibuar Mounty	the study contact lenses in place.	
		For near measurements use the ETDRS	
		2000 Series Chart 1 or 2.	
3.16.	Dispensing	The lenses may be dispensed for 6-8 days, if	
	Criteria	the following criteria are met:	
		Distance Snellen acuity equal to or better	
		than 20/30 OU	

	Visit 3: Treatment 1 Follow-Up 2		
Step	Procedure	Details	
		 Subject must indicate that the vision is acceptable. Subject must indicate that the comfort of the lenses is acceptable. Lenses must have an acceptable toric and general lens fit. 	
3.17.	Dispensing	Only enough lenses will be dispensed to the subject to wear for the required number of days until their follow-up visit. No additional lenses will be dispensed.	
3.18.	Subject Instructions	 Instruct the Subject on the following: The lenses will be worn on a daily disposable wear basis. Instruct the subject to bring back all unworn study lenses. Instruct the subject no cleaning or disinfecting solutions will be used for this lens type. If determined necessary by the Investigator sterile non-preserved rewetting drops may be dispensed to be used as needed for dryness. Subjects will be instructed to wear lenses for a minimum of 6 hours a day, every day between visits. One missed day of lens wear between visits is acceptable. Subjects will be instructed to wear study lenses to the next visit. It is not required that they have worn lenses for 6 hours on the day of the visit. Subjects will be instructed to wear their glasses when not wearing the study lenses. Subjects will be instructed to bring their spectacles with distance vision correction, or their habitual contact lenses to the final visit. 	
3.19.	Schedule	The subject will be scheduled to return for	
	Follow-up	their follow-up appointment in 7±1 days.	

VISIT 4

The subjects must present to Visit 4 wearing the study lenses.

	Visit 4: Treatment 1 Follow-Up 3		
Step	Procedure	Details	
4.1.	Adverse Events and Concomitant Medications Review	Review any changes to the subject's medical history or concomitant medications from the previous study visit. Record any changes, and any adverse events.	
4.2.	Wear time and Comfortable Wear time (Study Lenses)	Record the average wearing time and comfortable wearing time with the study lenses.	
4.3.	Compliance	Confirm compliance with the prescribed wear schedule.	
4.4.	Collect unworn lenses (if applicable)	The subject will return any unworn lenses.	
4.5.	PRO (CLUE and MRD) and CLDEQ-8 Questionnaires	The subject will respond to the Follow-Up PRO (CLUE and MRD) and Dry Eye Questionnaires.	
4.6.	Subject Reported Ocular Symptoms	Subjects will respond to a verbal open-ended symptoms questionnaire.	
4.7.	Subjective Acceptance	Record whether the subject's distance and near vision with the lenses is acceptable.	
4.8.	Entrance Distance and Near Visual Acuity	Record the distance and near Snellen visual acuity (OD, OS, OU) to the nearest letter with the study contact lenses in place. For near measurements use the ETDRS 2000 Series Chart 1 or 2.	
4.9.	Binocular Distance Over-refraction and Distance Visual Acuity	Perform a binocular over-refraction and record the OD and OS results and distance visual acuity. Note: No lens changes are allowed based on the over-refraction.	Appendix G
4.10.	Toric Fit Evaluation	 Record: The rotational position to the nearest degree Lens stability with blink Toric fit acceptable or unacceptable Toric lens fit will be unacceptable if lenses rotated more than 30 degrees, or lens stability is worse than 5 degrees movement with blink. If toric fit is unacceptable, remove, store, and label the lenses, and 	

	Visit 4: Treatment 1 Follow-Up 3			
Step	Procedure	Details		
		proceed to final evaluation.		
4.11.	Lens Fit Assessment	Evaluate and grade lens centration, primary gaze movement, upgaze movement and tightness (push-up test). • The subject should not proceed to wear the lenses if any of the following is		
		 observed: presence of limbal exposure (appearance of clear cornea) in any gaze presence of edge lift presence of unacceptable movement (excessive or insufficient) in all three movement categories (primary gaze, upgaze, and push-up). 		
		If either lens is deemed unacceptable, the subject will be discontinued from the study. Remove the lenses, perform a slit-lamp evaluation, and complete the Final Evaluation form.		
4.12.	Visual Performance Distance (4M) Intermediate (64 cm) Near (40 cm)	Visual performance will be recorded OD, OS, and OU for the following: Distance, Bright Illuminance ETDRS Charts 4M-HC#1, HC#2, HC#3 and LC#1, LC#2 and LC#3 Near, Bright Illuminance Reduced Guillon-Poling Charts High Contrast and Low Contrast Intermediate (64 cm) and Near (40 cm).		
		Distance, Dim Illuminance (with Distance goggles) ETDRS Charts 4M-HC#4, HC#5, HC#6 Near, Dim Illuminance (with Near goggles) Reduced Guillon-Poling charts High Contrast Intermediate (64 cm) and Near (40 cm). Note: The room illuminance must be between 7.3 and 7.9 EV.		

	Visit 4: Treatment 1 Follow-Up 3				
Step	Procedure	Details			
		 Distance, HC-1 Chart luminance Acceptable EV Range 10.5-10.7. Guillon-Poling, Near Chart Luminance Acceptable EV Range 10.8-11.1. Do not use the Mesopic filter for Dim luminance (Dim luminance will be simulated by using the goggles). 			
4.13.	Lens Removal	Have the subject remove the study lenses. Temporarily store the worn lenses until Biomicroscopy has been completed. If no adverse event or PQC was recorded, the worn lenses may be discarded.			

FINAL EVALUATION

The final evaluation will ordinarily take place immediately following the last scheduled follow-up visit per the study protocol. It may also take place at any point the subject discontinues the study or is terminated from the study.

	Final Evaluation				
Step	Procedure	Details			
F.1	Final Exam Form	Indicate if the subject completed the study successfully. If subject discontinued from the study, indicate the reason.			
F.2	Biomicroscopy	FDA Slit Lamp Classification Scale will be used to grade the findings and determine eligibility. If the clearance of the fluorescein needs to be expedited, preservative-free rewetting drops or saline may be instilled.			
F.3	Subjective spherocylindrical Refraction	An optimal, binocular balanced distance sphero-cylindrical refraction will be performed. Record the refraction and distance visual acuity (OD, OS, OU) to the nearest letter.			
F.4	Exit Distance Visual Acuity	Record the distance Snellen visual acuity (OD, OS, OU) to the nearest letter, and the type of visual correction being worn (habitual lenses, distance spectacles or unaided).			

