2.2. Endpoints

Primary Endpoints
Visual Acuity (logMAR)

Multiple assessments of binocular and monocular visual acuity will be made during the study, but the binocular measurements made at the 2-week follow-up evaluation using high contrast letters in bright illuminance conditions will be the primary endpoint. At distance (4 meters), VA is assessed using ETDRS Charts; while near (40 cm) and intermediate (64 cm) assessments will be made using reduced Guillon-Poling charts. Visual acuity will be measured using high and low contrast charts in bright illuminance conditions. Visual acuity will also be measured using high contrast charts in dim illuminance conditions created by the use of goggles. See in Appendix H for details regarding the collection of visual acuity (logMAR).

CLUE Vision Score

Subjective quality of vision will be assessed using the Contact Lens User Experience (CLUETM) questionnaire after approximately 2-weeks of wear. CLUE is a validated patientreported outcomes questionnaire to assess patient-experience attributes of soft, disposable contact lenses (comfort, vision, handling, and packaging) in a contact-lens wearing population in the US, ages 18-65. Derived CLUETM scores using Item Response Theory (IRT) follow a normal distribution with a population average score of 60 (SD 20), where higher scores indicate a more favorable/positive response with a range of 0-120. A 5-point increase in an average CLUETM score translates into 10% shift in the distribution of scores for population of soft contact lens wearers.⁵

Secondary Endpoints

- CLUE Vision Scores, change from baseline to 2-week follow-up
- CLUE Comfort Scores, change from baseline to 2-week follow-up
- CLUE Handling Scores, change from baseline to 2-week follow-up

Other Exploratory endpoints:

- Percentage of eyes with an unacceptable lens fit during the study
- Percentage of lens fits with rotation stability within 5 degrees at 15 minutes after insertion at the fitting visit
- Percentage of lens fits with absolute rotation error within 10 degrees at 15 minutes after insertion at the fitting visit
- Percentage of eyes with Grade 3 or 4 findings during the post-fit period.

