8.2. Withdrawal/Discontinuation from the Study

A subject will be withdrawn from the study for any of the following reasons:

- Subject death during the study period.
- Subject withdrawal of consent.
- Subject not compliant to protocol
- Subject lost to follow-up.
- Subject no longer meets eligibility criteria (e.g. the subject becomes pregnant).
- Subject develops significant or serious adverse events causing discontinuation of study lens wear.
- Subjects who have experienced a Corneal Infiltrative Event (CIE).
- Investigator's clinical judgment regarding the subject safety reasons (that it is in the best interest of the subject to stop treatment).
- Subject missed any study visit.
- Subject not compliant with study lens wear schedule.
- Subject not successfully dispensed due to lack of efficacy and safety including poor vision, poor comfort or unacceptable fit.

For discontinued subjects, the Investigator will:

- Complete the current visit (scheduled or unscheduled).
- Complete the Final Evaluation, indicating the reason that the subject was discontinued from the study.
- Record the spherocylindrical refraction with best corrected distance visual acuity.
- Collect used test article(s) (worn or brought to the visit) from the subject and discard them, unless otherwise stated in Section 7.2.
- Collect all unused test article(s) from the subject.
- Make arrangements for subject care, if needed, due to their study participation

An additional subject may be enrolled if a subject discontinues from the study prematurely.

In cases where a subject is lost to follow-up, every possible effort must be made to contact the subject and determine the reason for discontinuation/withdrawal. The measures taken to follow up must be documented including two written attempts and a certified letter (or equivalent) as the final attempt.

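### At Visit 4 a failed fit check removes the lenses before the primary logMAR test, so an attending subject can give a CLUE score but no primary acuity

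*Combined protocol and SAP*

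**What the plan says.** Hypotheses are numbered here as in Section 2.3: H1 and H2 are CLUE vision, H3 distance, H4 intermediate and H5 near acuity.

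Section 2.2 sets the acuity endpoint: "the binocular measurements made at the 2-week follow-up evaluation using high contrast letters in bright illuminance conditions will be the primary endpoint". The 2-week follow-up is Visit 4. The Visit 4 steps in Section 7.2 run in this order:

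- Step 4.5, CLUE: "The subject will respond to the Follow-Up PRO (CLUE and MRD) and Dry Eye Questionnaires".
- Step 4.8, entrance acuity on a Snellen scale: "Record the distance and near Snellen visual acuity (OD, OS, OU) to the nearest letter with the study contact lenses in place".
- Step 4.9, binocular over-refraction.
- Step 4.10, toric fit: "Toric lens fit will be unacceptable if lenses rotated more than 30 degrees, or lens stability is worse than 5 degrees movement with blink". On failure: "If toric fit is unacceptable, remove, store, and label the lenses, and" the subject goes to final evaluation.
- Step 4.11, general lens fit (limbal exposure, edge lift, movement): "If either lens is deemed unacceptable, the subject will be discontinued from the study", and the lenses come out.
- Step 4.12, the logMAR test at 4 m, 64 cm and 40 cm: "Visual performance will be recorded OD, OS, and OU for the following".

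For discontinued subjects Section 8.2 instructs the investigator: "Complete the current visit (scheduled or unscheduled").

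The acuity model in Section 14.5 uses the 2-week measurements, with chart position as the only required fixed effect. Section 14.9 does not impute missing values, and calls for multiple imputation as a sensitivity analysis only if dropout exceeds 15%.

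**The concern.** The fit check decides whether the primary acuity is measured at all, and what it checks is plausibly related to acuity. For a toric lens, rotation or instability is a natural cause of blur. A subject who is present, wearing the lens and measurable would be lost from the acuity analysis because of how the lens sits that day, after already giving the primary CLUE score.

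This is a single-arm study tested against fixed thresholds, so no control arm suffers the same loss. If the lost subjects see worse than the rest, the observed mean logMAR is too low (too good) and the test leans towards success.

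At the earlier visits the check comes before further dispensing. At Visit 4 nothing more is dispensed (Table 3) and step 4.13 removes the lenses in any case, so testing acuity after the fit grade serves no evident purpose there.

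The conflict with Section 8.2 adds a second problem. One site may stop at 4.10 and another may try to finish the visit, so whether the endpoint exists could depend on the site.

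**Working it through.** **1. Can the missing value be recovered?** Each possible source was checked.

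- Final Evaluation: step F.4 records Snellen distance acuity with habitual lenses, spectacles or no correction. It has no logMAR and no study-lens acuity.
- Acuity model (14.5): it uses 2-week data only, so the Visit 3 logMAR does not enter. All three chart positions are measured at 4.12, so a subject stopped at 4.10 or 4.11 contributes no rows.
- Imputation (14.9): none in the main analysis. The sensitivity trigger is more than 15%; 12 of 80 is exactly 15.0% and would not set it off. Whether a fit failure at the last visit counts as dropout is not stated.
- Section 8.2: completing the visit cannot yield study-lens acuity once the lenses are out.

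No planned analysis recovers the value.

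**2. Inputs.** From Table 6 and Section 2.3: distance mean -0.048, SD 0.0943, threshold 0.00; intermediate -0.015, SD 0.1183, threshold 0.17; near 0.097, SD 0.1318, threshold 0.17. Target completers: 80 (Section 14.2). To confirm the distance inputs, a one-sample t-test with difference 0.048, SD 0.0943, N = 42 and one-sided alpha 0.01 gives 80.6% power, the Table 8 figure. (The two-sided 0.01 that Section 14.2 describes gives 72.2%; that is a separate matter.)

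**3. Distance of each historical mean from its threshold at N = 80**, with SE = SD/√80:

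- H3: 0.048 / 0.01054 = 4.6 SE
- H4: 0.185 / 0.01323 = 14.0 SE
- H5: 0.073 / 0.01474 = 5.0 SE

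H4 is practically insensitive. H3 is the most exposed, then H5.

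**4. Shift in the observed mean.** Suppose k of 80 subjects fail the Visit 4 fit check and their acuity is d logMAR worse than that of the others. The tested subjects' mean is then better than the all-subject mean by k × d / 80. Neither k nor d is in the documents; the ranges 1 to 4 and 0.05 to 0.20 are assumptions.

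- Low end: 1 × 0.05 / 80 = 0.0006 logMAR, about 1% of the 0.048 gap for distance.
- High end: 4 × 0.20 / 80 = 0.010 logMAR, about 21% of that gap.

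**5. False success at the threshold.** Set the true all-subject mean exactly at the threshold. Under the Section 14.5 rule (upper 95% limit below the threshold) the nominal rate is 2.5%. With n = 80 - k tested subjects and noncentrality (k × d / 80) × √n / SD, the noncentral t gives:

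| Failures k | d (logMAR) | Shift | H3 | H5 |
|---|---|---|---|---|
| 1 | 0.05 | 0.0006 | 2.9% | 2.8% |
| 2 | 0.10 | 0.0025 | 4.2% | 3.6% |
| 2 | 0.20 | 0.0050 | 6.7% | 5.2% |
| 4 | 0.20 | 0.0100 | 14.8% | 9.6% |

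Section 14.4 calls for Bonferroni adjustment, although the rules in 14.5 use 95% limits. With a 99% interval (nominal 0.5%) the last row becomes 4.7% for H3 and 2.7% for H5.

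**6. If the tested subjects match Table 6**, how poor must the untested ones be to reverse the result under the 95% rule? H3 would be lost if 4 failures averaged 0.35 logMAR or 8 averaged 0.18. H5 would need 0.72 or 0.46, and H4 1.82 or 1.07.

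**The case against.** The strongest reply is that this will seldom happen and seldom matter. Subjects reaching Visit 4 have passed the same criteria at Visits 1, 2 and 3, and are dispensed lenses at Visit 3 only if toric and general fit are acceptable (step 3.16). The upper figure needs four new failures at the last visit, each 0.20 logMAR worse binocularly, and a true mean exactly at the threshold. That objection stands as to size and puts the likely effect near the low end. It does not remove the gap: a fresh lens is worn each day, and the protocol itself repeats the check.

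The link to acuity is also not uniform. It is plausible for rotation and blink instability, but less certain for edge lift, limbal exposure or movement. The endpoint is binocular, and one failing eye is enough to trigger step 4.11. A reader might infer that a lens at the 30-degree limit leaves residual cylinder as large as its own cylinder power. The documents do not support that: rotation is measured from a vertical reference line, the fitting steps allow another axis to be chosen to compensate, and the second toric trigger is only 5 degrees of movement.

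A reader might also infer that every such subject is recorded as discontinued and leaves the Per-Protocol set. Discontinuation is explicit only in step 4.11. Step 4.10 says only that final evaluation follows, as it ordinarily does after Visit 4. Section 14.5 names no primary population. If Per-Protocol were used and the subject excluded, CLUE would be lost too, so the contrast between CLUE and acuity holds for an ITT-type analysis. The acuity selection arises under either population.

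The loss would be partly visible, since unacceptable fit is summarised by visit (14.7) and missing counts are tabulated (14.9). Visit 3 logMAR and Visit 4 entrance Snellen acuity also exist for these subjects. But visibility is not correction, and no planned analysis uses those values for H3 to H5.

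**Conclusion.** The point holds. Followed as written, the Visit 4 steps discard the primary acuity of an attending subject on a criterion plausibly tied to acuity, and they contradict Section 8.2. The direction tends to favour success, mainly for H3 and less for H5.

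Its size cannot be established from the documents. Under the assumed ranges the H3 false-success rate at the threshold goes from 2.5% to between about 2.9% and 15%, more likely near 2.9%. These are rates for one hypothesis with the true mean at its threshold. Section 2.3 requires all five primary hypotheses to be met, so they are not study-level error rates. It would be too strong to say that all three acuity hypotheses are materially biased: at the historical means H4 is about 14 SE from its threshold, and H3 reverses only if the failures see very poorly. The change is worth making because it is cheap and closes the gap completely for subjects who attend Visit 4 and would otherwise be stopped at a fit check.

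**What to change.** - In the Visit 4 table of Section 7.2, place Visual Performance (now 4.12) before Toric Fit Evaluation and Lens Fit Assessment (now 4.10 and 4.11). Leave the fit criteria and the action on failure as written.
- State in Section 14.5 that logMAR acuity recorded at Visit 4 counts in the H3 to H5 analysis whatever the Visit 4 fit grade.
- Reconcile the Visit 4 fit steps with the instruction in Section 8.2 on completing the current visit, so that all sites act alike.

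The cost is a reordered visit script and eCRF. No procedure or subject is added.

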7.3. Unscheduled Visits

If, during the investigation, a subject requires an unscheduled visit to the clinical site, the following information will be collected at a minimum:

- Chief complaint prompting the visit. If the reason is an adverse event, the applicable eCRF for the adverse event must be completed and subject record completed as appropriate
- Date and time of the visit and all procedures completed at the unscheduled visit
- Review of adverse event and concomitant medications
- Documentation of any test article dispensed or collected from the subject, if applicable
- Slit lamp findings (using the Slit Lamp Classification Scale)

If the Investigator withdraws a subject from the study, the final study visit case report forms must be completed indicating the reason(s) why the subject was withdrawn. The subject record must be completed documenting the date and primary reason for withdrawal and the study CRA notified.

Any ocular and non-ocular Adverse Events that are ongoing at the time of the study visit will be followed by the Investigator, within licensure, until they have resolved, returned to pretreatment status, stabilized, or been satisfactorily explained. If further treatment i.e., beyond licensure is required, the subject will be referred to the appropriate health care provider.

The following information will be collected during an unscheduled visit.

	Unscheduled Visit				
Step	Procedure	Details			
U.1	Reason for	Indicate if the only reason for the visit is that			
	unscheduled visit	the subject requires additional test articles. If			
		the reason is other than resupply of			
		previously dispensed lenses, specify the			
		reason for the visit.			
U.2	Chief Complaints (if	Record the subject's chief complaints for			
	applicable)	reasons for the unscheduled visit.			
U.3	Adverse Events and	Review any changes to the subject's medical			
	Concomitant	history or concomitant medications from the			
	Medications Review	previous study visit. Record any changes, and			
	(if applicable)	any adverse events.			
U.4	Entrance VA (if	Record the distance Snellen visual acuity			
	applicable)	(OD, OS, OU) to the nearest letter, and the			
		type of visual correction being worn (study			
		lenses, habitual lenses, distance spectacles or			
		unaided).			
U.5	Subjective Sphero-	Perform bare-eye subjective spherocylindrical			
	cylindrical	refraction with a phoropter (adopt the			
	Refraction (if	maximum plus to maximum visual acuity			
	applicable)	(MPMVA) approach and use the duo-chrome			

_	Unscheduled Visit				
Step	Procedure	Details			
Бюр	Troccure	test for binocular balancing) and record the best corrected distance visual acuity to the nearest letter (OD, OS).			
U.6	Slit Lamp Biomicroscopy (if applicable)	FDA Slit Lamp Classification Scale will be used to grade the findings. If the clearance of the fluorescein needs to be expedited, preservative-free rewetting drops may be instilled.			
U.7	Dispensing (if applicable)	If the subject requires additional lenses to complete the wear period and is eligible to do so, provide additional lenses per the dispensing instructions given in the detailed study procedures.			
U.8	Toric Fit Evaluation (if applicable)	 After lens settling, record: The rotational position to the nearest degree Lens stability with blink Lens stability with eye versions Toric fit acceptable or unacceptable Toric lens fit will be unacceptable if lenses rotated more than 30 degrees, or lens stability is worse than 5 degrees movement with blink. If toric fit is unacceptable, remove, store, and label the lenses, and proceed to final evaluation. 			
U.9	Lens Fit Assessment (if applicable)	Evaluate and grade lens centration, primary gaze movement, upgaze movement and tightness (push-up test). • The subject should not proceed to wear the lenses if any of the following is observed: • presence of limbal exposure (appearance of clear cornea) in any gaze • presence of edge lift • presence of unacceptable movement (excessive or insufficient) in all three movement categories (primary gaze, upgaze, and push-up). If either lens is deemed unacceptable, the subject will be discontinued from the study.			

	Unscheduled Visit				
Step	Procedure	Details			
		Remove the lenses, perform a slit-lamp			
	evaluation, and complete the Final				
		Evaluation form.			
U.10	Exit Visual Acuity	Record the distance Snellen visual acuity			
	(if applicable)	(OD, OS, OU) to the nearest letter, and the			
type of visual correction being worn (s		type of visual correction being worn (study			
		lenses, habitual lenses, distance spectacles or			
		unaided).			

